10.8.2 Primary Analysis(es)

Product safety will include summaries overall of the incidence of treatment-emergent adverse events, incidence of product-related urogenital adverse events, and incidence of other findings from pelvic examinations (e.g., ulcerations, abrasions, edema, and bleeding). To compare the incidence of TEAEs between the two study arms, Chi-squared test for independence or Fisher's exact test will be used as per the assumptions.

Changes from baseline in clinical laboratory endpoints will be summarized. Shift tables will be produced where relevant.

Evaluation for Study Objectives:

Study objectives will be evaluated by clinical review of descriptive summaries and graphical displays.

Descriptive Statistics:

Categorical variables will be summarized by frequencies and percentages. Continuous variables will be summarized by mean (SD) when found normally distributed. Median (IQR) will be used otherwise. Normality will be assessed graphically by Q-Q plots and statistically by Shapiro-Wilk test for normality. Categorical variables will be summarized by frequency and percentages (e.g. incidence of adverse events).

In addition to descriptive summaries, pharmacokinetic analysis will include time concentration curves for each participant and pooled by sample timepoint group.

To assess for the comparability between the two arms of the study at baseline, t-test or Mann-Whitney test will be used to assess for the differences in continuous variables as appropriate based on the normality assumption. While chi-squared test for independence or Fisher's exact test will be used for categorical variables as appropriate.

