10.8.3 Secondary and Exploratory Analyses

Safety:

To assess for the difference in subclinical safety endpoints between TAF/EVG and placebo group, the incidence of different TEAES will be calculated and risk ratio will be estimated. Chi-squared test or fisher exact test will be used as appropriate. A binary variable will be created for each one of the TEAEs of interest, then Multivariable logistic regression will be used to assess for the difference in the occurrence of TEAEs. In this model the risk ratio will be calculated instead of the odds ratio using Stata command (*oddrisk*).

While for quantitative laboratory safety parameters, mixed-effect design will be used to assess for the changes in these parameters over time within the TAF/EVG and placebo group separately

and will assess for the differences in the laboratory parameters between the TAF/EVG and placebo group.

PK and PD:

PK analysis will include descriptive statistics by sample time point of EVG, TFV, and TAF concentrations for all plasma, CVT, and CVF sample types, in addition to TFV-DP concentrations from CVT samples.

PD endpoints will be summarized using descriptive statistics by time point as well as changes from baseline. Estimates and 95% confidence intervals will be provided. Analysis will include summaries of anti-HIV and anti-HSV activity in CVF, and AUC (Area under the curve) and/or SOFT endpoints will be performed to determine if there is a difference between infection of samples collected at baseline and after treatment. Anti-viral activity in CVF (the change in HIV-1 and HSV infections for samples obtained on treatment vs. baseline) will be summarized.

Changes from baseline in clinical laboratory endpoints will be assessed using paired t test or Wilcoxon signed rank test based on the normality of the data. Repeated measures ANOVA or Friedman test for repeated measures will be used to assess the change from baseline through the endpoint.

Mixed effect-design will be used to compare within and between participants changes for different PK and PD endpoints from baseline to endpoint.

Disintegration and acceptability:

Disintegration endpoints will be summarized descriptively.

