15 APPENDICES

APPENDIX I: SCHEDULE OF STUDY VISITS AND EVALUATIONS

[figure not shown]
	Screening Visit 1	Enrollment Visit 2	Random- ization Visit 3	Post 3 rd Dose Visit 4	4 th & 5 th Dose Visits 5-6	Post Last Dose Visits 7a,b,c	SEV Visit 8	
			10-14 days post V2	3 days post V3	V5 is 10- 14 days post V4	Participants attend only 1 timepoint 11, 12 or 13 days post V6	10 days post V7	
ADMINISTRATIVE AND REGULATORY								
Informed consent process	X							
Assign a unique PTID	X							
Assess/confirm eligibility	X	X						
Collect/review/update locator information	X	X	X	X	X	X	X	
Provide reimbursement	X	X	X	X	X	X	X	
Schedule next visit/contact	*	*	X	X	X	X		
Randomization (1:1) study product (after HIV and pregnancy tests)			X					
Randomization (1:1:1) PK tail sampling (after HIV and pregnancy tests)			X					
BEHAVIORAL/COUNSELING								
Protocol adherence counseling	X	X	X	X	X	X		
HIV pre and post/ risk reduction counselling	X	X	X			X	X	
Demographic information	X							
Behavioral questionnaire		X				X		
Product use questionnaire		X	X	X		X		
IDI (subset)							X	
CLINICAL								
Physical exam (directed after Screening)	X	*	*	*	*	*	*	
Vital signs and weight		X	X	X	X	X	X	
Collect/review/update medical and menstrual history	X	X	X	X	X	X	X	
Pelvic exam (bimanual exam at Screening)	X	X	X	X	X	X	X	
Assess AEs			X	X	X	X	X	
Assess CMs	X	X	X	X	X	X	X	
LABORATORY								
URINE	Pregnancy test	X	X	X	*	*	X	X
	Urine dipstick/ urinalysis	X	*	*	*	*	*	*

		Screening Visit 1	Enrollment Visit 2	Random- ization Visit 3	Post 3 rd Dose Visit 4	4 th & 5 th Dose Visits 5-6	Post Last Dose Visits 7a,b,c	SEV Visit 8
				10-14 days post V2	3 days post V3	V5 is 10- 14 days post V4	Participants attend only 1 timepoint 11, 12 or 13 days post V6	10 days post V7
BLOOD	HIV test	X	X	X			X	X
	HBsAg	X						
	CBC with platelets, Chemistries	X					X	
	HSV-2, Syphilis	X					X	
	Plasma for archive		X					
	PK (Plasma): TAF, TFV, EVG				X	X	X	X
PELVIC	GC, CT, TV testing	X	*	*	*	*	X	*
	Saline/KOH wet mount for candidiasis &/or BV	*	*	*	*	*	*	*
	PSA (semen marker)		X	X	X	X	X	X
	Pap smear	*						
	Gram stain for Nugent score, Vaginal pH		X	X	X	X	X	X
	Vaginal microbiota (16S RNA microbiome)			X	X	X	X	X
	CVF for TAF, TFV, EVG PK levels			X	X	X	X	X
	CVF for Anti-HSV2, Anti-HIV		X	X	X	X	X	X
	CVL (secreted soluble markers)		X	X	X	X	X	X
	BXV for PK – TAF, TFV, EVG, TFV-DP				X		X	
	BXV for IHC		X				X	
	BXC for HIV (EVMS only)		X		X		X	
REC TAL	RF for TAF, TFV, EVG PK levels (if participant agrees)			X	X	X	X	X

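### Change in clinical laboratory values is tested pre/post without a placebo contrast, alongside a between-arm mixed model and a descriptive summary, with no order of precedence among them

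*Protocol*

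**What the plan says.** The Protocol treats change in laboratory values in three places.

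- **Section 10.8.2 (primary analyses)** describes it: "Changes from baseline in clinical laboratory endpoints will be summarized. Shift tables will be produced where relevant". The same section says how conclusions are reached: "Study objectives will be evaluated by clinical review of descriptive summaries and graphical displays".
- **Section 10.8.3, Safety**, models it. The rule covers numeric safety laboratory results: "mixed-effect design will be used to assess for the changes in these parameters over time within the TAF/EVG and placebo group separately". The model also "will assess for the differences in the laboratory parameters between the TAF/EVG and placebo group".
- **Section 10.8.3, PK and PD**, tests it: "Changes from baseline in clinical laboratory endpoints will be assessed using paired t test or Wilcoxon signed rank test", the choice depending on normality. The next sentence adds repeated measures ANOVA or Friedman for change from baseline through the endpoint. Neither sentence names an arm or a comparison with placebo.

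Appendix I has a row for "CBC with platelets, Chemistries" that is marked only at Screening (Visit 1) and at Visit 7. Tables 1 and 7 agree. Section 10.3 words the primary hypothesis as no clinically significant change in safety endpoints from baseline.

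**The concern.** The trial has a placebo arm so that product effects can be told apart from whatever else happens between Screening and Visit 7. A paired test does not use that arm, so any drift common to both groups enters it as change.

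Shared drift is plausible from the Protocol's own design. The Visit 1 panel is both the eligibility screen and the only scheduled pre-dose value, and exclusion criterion 12 removes women with Grade 2 or higher laboratory abnormalities. Selecting on the baseline value invites regression to the mean in both arms. The interval is also long, and blood draws and biopsies fall within it.

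Because the hypothesis is worded as change from baseline, a reader could take the pre/post p-value as its natural test. If that p-value and the randomized comparison disagree, the Protocol does not say which one counts. At stake is a false laboratory signal, or an argument over one, in a Phase 1 safety trial.

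**Working it through.** **Is there a plan figure to reproduce?** No. The only calculation in the Protocol is the sample size in section 10.4, and this point does not rest on it.

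**1. Number of time points and length of interval.** CBC and chemistries have two scheduled values, at Visits 1 and 7. Summing the longest stated intervals:
- Visit 1 to 2: 8 weeks = 56 days
- Visit 2 to 3: 14 days
- Visit 3 to 4: 3 days
- Visit 4 to 5: 14 days
- Visit 5 to 6: 2 days
- Visit 6 to 7: 13 days

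The total is 56 + 14 + 3 + 14 + 2 + 13 = 102 days, about 14.6 weeks. Blood is drawn at Visits 2 to 6, and biopsies are taken at Visits 2 and 4, before the Visit 7 panel.

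**2. What the repeated-measures tests add with two values.** With two time points, the repeated measures ANOVA F statistic equals the square of the paired t statistic. In a simulated data set of 30 pairs, F = t² = 5.72 and p = 0.0234 for both. Friedman on two time points uses only the direction of each change, so it reduces to a sign test. For CBC and chemistries, repeated measures ANOVA therefore repeats the paired t test, and Friedman uses less of the data.

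**3. How often the paired test is significant with an inert product.** Inputs from the Protocol: 30 women per arm (section 10.5) and a 5% level (section 10.4), taken here as two-sided. Assumptions, because the documents give no SD, correlation or drift: the same shift δ in both arms (in SD units of a single measurement), correlation ρ between the two values, normal data and no product effect.

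SD of change = √(2(1 − ρ)). Noncentrality = δ / SD of change × √n. The critical t on 29 df is 2.045.

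| δ | ρ | SD of change | Noncentrality (n = 30) | Active-arm paired t significant |
|---|---|---|---|---|
| 0.2 | 0.5 | 1.000 | 1.095 | 19% |
| 0.2 | 0.7 | 0.775 | 1.414 | 28% |
| 0.3 | 0.5 | 1.000 | 1.643 | 36% |
| 0.3 | 0.7 | 0.775 | 2.121 | 54% |

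The shared shift cancels in the between-arm comparison of change. In 40,000 simulated trials per setting, that test stayed at 4.8% to 5.2% for every drift tried, from 0 to 0.8 SD of the change score.

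**4. How often the two analyses disagree.** From the same simulation with 30 per arm, this is the share of trials in which the active-arm paired test is significant and the between-arm test is not. Drift here is in SD units of the change score.

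| Drift | Disagreement |
|---|---|
| 0 | 3.3% |
| 0.2 | 16.5% |
| 0.3 | 33% |
| 0.5 | 73% |

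**5. Precision.** The variance of the arm contrast under ANCOVA, relative to a change-score analysis, is (1 − ρ²) / (2(1 − ρ)) = (1 + ρ)/2. That is 0.75 at ρ = 0.5 and 0.85 at ρ = 0.7, a saving of 25% and 15%.

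**The case against.** The case on the other side has real force.

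- **No rule turns a paired p-value into a finding.** Section 10.8.2 leaves objectives to clinical review of descriptive output, and the hypothesis concerns clinically, not statistically, significant change. This stands. A reader might infer that the plan will declare a product effect from the pre/post test, but the text does not say so.
- **The rules overlap rather than contradict.** All three analyses can be reported, and the randomized comparison is explicitly planned. This stands too, so calling the rules conflicting would be too strong. What remains is that uncontrolled tests are prescribed next to the controlled one with no order between them. A statistical analysis plan could set that order, but the tests are fixed in the Protocol itself.
- **The primary analysis is untouched.** Grade 2 or higher adverse events are compared between arms by chi-squared or Fisher's exact test. Agreed.
- **Not every laboratory measure has two values.** Section 7.10 also lists Nugent score and pH under the local laboratory, and Appendix I schedules them from Visit 2 to Visit 8. For these, a repeated-measures test is not redundant, and a Visit 7 ANCOVA would discard data. Agreed; the redundancy argument is confined to CBC and chemistries.
- **The mixed model's form is not given.** A reader might infer that it ignores the pre-dose value and is inefficient. The Protocol does not say that, and a model with a common baseline mean would have essentially ANCOVA precision. The 15% to 25% saving is relative to a change-score analysis only and is secondary.
- **The drift is assumed.** True. The suggested sources bear more obviously on CBC than on AST, ALT or creatinine. With no drift the paired test holds its 5% level.

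**Conclusion.** The point holds as a flaw in a secondary safety analysis. Section 10.8.3 prescribes pre/post tests of laboratory change that cannot separate product effect from shared drift, although the same section plans the comparison that can, and no precedence is set. For CBC and chemistries the additional repeated-measures tests contribute nothing useful.

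The size depends on assumptions the documents cannot confirm. With a shared shift of 0.2 to 0.3 SD, a correlation of 0.5 to 0.7 and an inert product, an active-arm paired test is significant in about 19% to 54% of trials, against 5% between arms. The point does not reach the sample size or the primary adverse event comparison, and conclusions remain subject to clinical review. It is worth correcting because the change is specific and nearly free.

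**What to change.** In section 10.8.3, remove the paired t/Wilcoxon and repeated measures ANOVA/Friedman sentences for clinical laboratory endpoints, or label within-arm change as descriptive only, alongside the shift tables in 10.8.2.

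Name the between-arm difference as the sole inferential analysis, adjusted for the pre-dose value and site, with a 95% confidence interval:
- for CBC and chemistries, ANCOVA of the Visit 7 value;
- for laboratory measures taken at several visits, the mixed model already planned, with baseline adjustment stated.

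If the sentence under PK and PD was meant for PD endpoints, correct it to say so.

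The cost is a change of wording and slightly less analysis. No new data, visits or participants are needed.

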Participants will provide a urine sample for a UPT and undergo HIV screening prior to randomization. Participants will also complete a brief product use assessment and undergo baseline pre-insertion sample collection of CVL, CVF for PK, PD, and vaginal microbiota, and (if participant agrees) RF for PK. Provided they have negative HIV and pregnancy test results, participants will be randomized (1:1) to receive TAF/EVG versus placebo vaginal insert. Participants will also be randomized (1:1:1) into three time points for PK tissue sampling after the last dose (24, 48, or 72 hours post last dose).

Participants will then self-administer the first dose (single combination insert of TAF/EVG or placebo) in the clinic. Participant will be dispensed doses 2 and 3 for daily insertion at home.

Table 3: Randomization Visit

Randomization Visit – Visit 3		
Component		Procedures
Administrative and Regulatory		
 ● Confirm participation ● Conduct product assignment randomization (after HIV and pregnancy tests) ● Conduct PK tissue sampling randomization (after HIV and pregnancy tests) ● Review/update locator information ● Provide reimbursement ● Schedule next visit/contact
Behavioral/Counseling		
 ● Protocol requirements/prohibited vaginal and anal activity ● Pre- and post-test HIV counseling, and risk reduction counselling ● Initial product use assessment
Clinical		
 ● Review/update medical and menstrual history ● Assess adverse events (AE) and CM ● Pelvic exam pre-dosing ● Directed physical examination, if indicated ● Vital signs and weight ● Treat or prescribe treatment for RTI/UTI/STIs, if indicated ● Provide available test results
Laboratory	Urine	
 ○ Pregnancy test ○ Urine dipstick/urinalysis, if indicated
	Blood	
 ○ HIV
	Genital	
 ○ PSA test ○ Gram stain for Nugent score, pH ○ CVF for PK and PD ○ CVL for soluble markers ○ Vaginal microbiota ○ TV, GC, CT testing, if indicated ○ Saline/KOH wet mount for candidiasis and/or BV, if indicated
	Anorectal	
 ○ RF for PK (if participant agrees)

Randomization Visit – Visit 3	
Component	Procedures
Study Product/Supplies	
 • Self-insertion of 1st dose • Dispense doses 2-3 for home insertion

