	Anorectal	
 ○ RF for PK (if participant agrees)
Study Product/Supplies		
 ● Self-insertion of 5th dose ● Dispense doses for home insertion

7.3.4 24/48/72-hours Post Last Dose Visit – Visit 7

Visit 7 will take place either 11, 12 or 13 days after Visit 6. Visit 7 will be split into three timepoints: a) 24-hours post last dose, b) 48-hours post last dose, and c) 72-hours post last dose. Only a third of participants will attend each timepoint, depending on randomization at Visit 3. Participants will provide a urine sample for a UPT, a blood sample for safety tests, and undergo HIV/STI testing. Participants will also undergo sample collection of CVL, blood for PK, CVF for PK, PD, and vaginal microbiota, CVT for subclinical safety, PK and PD, (if participant agrees) RF for PK, and complete an acceptability questionnaire.

Table 7: 24/48/72-hours Post Last Dose Visit

24-hr/48-hr/72-hr Post Last Dose – Visit 7	
Component	Procedures
Administrative and Regulatory	
 ● Confirm participation ● Review/update locator information ● Provide reimbursement ● Schedule next visit/contact
Behavioral/Counseling	
 ● Comprehensive behavioral and product use questionnaire ● Protocol requirements/prohibited vaginal and anal activity ● Pre- and post-test HIV counseling, and risk reduction counselling
Clinical	
 ● Review/update medical and menstrual history ● Assess for AE and CM ● Pelvic exam ● Directed physical examination, if indicated ● Vital signs and weight ● Treat or prescribe treatment for RTI/UTI/STIs, if indicated ● Provide available test results

24-hr/48-hr/72-hr Post Last Dose – Visit 7		
Component	Procedures	
Laboratory	Urine	
 ○ Pregnancy test ○ Urine dipstick/urinalysis, if indicated
	Blood	
 ○ Plasma for PK ○ HIV, HSV-2*, Syphilis ○ CBC with platelets, Chemistries
	Genital	
 ○ PSA test ○ Gram stain for Nugent score, pH ○ TV, GC, CT testing ○ CVF for PK and PD ○ CVL for soluble markers ○ Vaginal microbiota ○ BXV for IHC ○ BXV for PK ○ BXC for HIV (EVMS only) ○ Saline/KOH wet mount for candidiasis and/or BV, if indicated
	Anorectal	
 ○ RF for PK (if participant agrees)

*HSV-2 results will not be provided to participants

7.3.5 Study Exit Visit (SEV) – Visit 8

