10.5 Randomization Procedures

Participants will be randomized (1:1) to receive either combination TAF/EVG or placebo vaginal insert. Participants will be randomized 1:1:1 to one of three timepoint groups for tissue sample collection post dosing.

Participants	Randomization Group
30	TAG/EVG insert
30	Placebo insert

Sample Collection Groups	Timepoints after Dosing
Timepoint group 1	24 hours (7a)
Timepoint group 2	48 hours (7b)
Timepoint group 3	72 hours (7c)

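### The 10.8.3 PK/PD mixed model gives the randomized 24/48/72 h sampling time no stated role and compares changes; for fluid antiviral activity it should model the time and adjust for the pre-dose value

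*Protocol*

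**What the plan says.** **The model.** Section 10.8.3 states: "Mixed effect-design will be used to compare within and between participants changes for different PK and PD endpoints from baseline to endpoint". It lists no model terms and does not say which visits are the baseline and the endpoint.

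**The design.** Section 10.5 states: "Participants will be randomized 1:1:1 to one of three timepoint groups for tissue sample collection post dosing". Section 7.3.4 adds: "Visit 7 will be split into three timepoints", and "Only a third of participants will attend each timepoint, depending on randomization at Visit 3". Plasma, CVF and vaginal tissue are all taken at the allotted time (Tables 7 and 9).

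**The summaries.** These keep the times apart. In 10.8.3, "PK analysis will include descriptive statistics by sample time point of EVG, TFV, and TAF concentrations", and "PD endpoints will be summarized using descriptive statistics by time point as well as changes from baseline". In 10.8.2 the PK output includes "time concentration curves for each participant and pooled by sample timepoint group".

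**Pre-dose samples.** CVF for antiviral activity is taken at Visit 2 (7.2.1) and again at Visit 3, where women "undergo baseline pre-insertion sample collection of CVL, CVF for PK, PD, and vaginal microbiota, and (if participant agrees) RF for PK". After dosing begins it is taken at Visits 4 to 8. By Table 9, plasma and tissue PK start only at Visit 4, so they have no pre-dose value.

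**The concern.** The insert is meant for on-demand use (2.6.2), so how long activity lasts after the last dose is a natural question. The randomization to 24, 48 and 72 hours makes a clean comparison with placebo possible at each time. The sentence that defines the comparison speaks of one endpoint and does not mention this factor. Followed literally at Visit 7, it gives one pooled arm difference, and any fall over the 48 hours is counted as unexplained variation among women in the active arm.

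The sentence also makes change the quantity compared. CVF activity is measured before randomization and dosing, so the pre-dose value could be used as an adjustment. Subtracting it whole carries its measurement noise into the comparison.

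At stake are the precision of the CVF activity comparison and whether the model yields any between-arm estimate at 48 or 72 hours.

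**Working it through.** **The plan's own figure.** The protocol gives no power or precision figure for this model. Its only sample-size figure (10.4) is 10 per arm per site for a 60% difference. That reproduces with the two-sided two-proportion formula at, for example, 0.2 v 0.8, but has no bearing here. The protocol gives no SD for CVF activity, no baseline correlation and no multiple-dose decay, so each result below rests on stated assumptions.

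**1. Change v baseline adjustment (CVF activity).** From 10.5: n = 30 per arm. Assumed: equal SD of 1 before and after dosing in both arms, correlation r of 0.3 to 0.6, true difference 0.6 SD, two-sided 5% test, normal approximation.

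- Variance of the arm difference in change: 4(1 − r)/n
- Variance of the baseline-adjusted difference: 2(1 − r²)/n
- Ratio: 2/(1 + r)

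| r | Change | Adjusted | Ratio | Power, change | Power, adjusted |
|---|---|---|---|---|---|
| 0.3 | 4 × 0.7/30 = 0.0933 | 2 × 0.91/30 = 0.0607 | 1.54 | 50% | 68% |
| 0.6 | 4 × 0.4/30 = 0.0533 | 2 × 0.64/30 = 0.0427 | 1.25 | 74% | 83% |

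**2. What a pooled Visit 7 contrast estimates.** With 1:1:1 allocation it estimates (d24 + d48 + d72)/3, where each d is the arm difference at that time. Differences of 1, 1, 1 and of 2, 1, 0 both average 1. The pooled figure cannot tell lasting activity from activity that has gone by 72 hours.

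**3. Effect on the standard error if activity declines.** Suppose a linear fall D over 24 to 72 hours in the active arm only, with residual SD s. Three equal groups at −D/2, 0 and +D/2 add D²/6 to the active-arm variance. The reported standard error of the arm difference is then multiplied by √(1 + D²/(12s²)).

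A simulation with 30 per arm, exactly 10 per arm per time, outcome SD 1 and r = 0.5 gave these mean reported standard errors:

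| Fall over 24–72 h | Change, no time group | Change, arm-by-time terms | Arm-by-time terms plus baseline |
|---|---|---|---|
| 0 | 0.257 | 0.257 | 0.225 |
| 1 SD | 0.268 | 0.257 | 0.225 |
| 2 SD | 0.298 | 0.257 | 0.225 |

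Omitting the group inflates the reported figure by about 4% at 1 SD, about 16% at 2 SD, and not at all with no decline. The actual spread of the change-score estimates was about 0.26 with or without the group terms, and the average stayed unbiased.

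The only decay information is for tenofovir concentration in vaginal fluid after a single dose (2.5.1): above 200,000 ng/mL to 24 hours and above 1,000 ng/mL to 7 days. If these two lower bounds are read as a log-linear fall (an assumption):

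- log10(200)/6 = 0.384 per day, so D = 0.767 log10, or 5.8-fold, over 48 hours
- added active-arm variance: 0.767²/6 = 0.098
- with assumed SDs of 0.6 and 0.4 log10: 0.098/0.36 = 27% and 0.098/0.16 = 61%
- standard error of an arm difference, assuming equal placebo variance: √(1 + 0.27/2) = 1.07 and √(1 + 0.61/2) = 1.14

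**4. Precision of time-specific contrasts.** About 10 v 10 women are expected at each time. Before baseline adjustment, the difference detectable with 80% power is 2.80 × √(2/10) = 1.25 SD, against 2.80 × √(2/30) = 0.72 SD for the average. For tissue p24, done at EVMS only, about 20 women over 2 arms and 3 times leave 20/6 = 3.3 per cell.

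**The case against.** The strongest reply is that the fault is read from silence. A mixed model can carry visit or sampling-group terms and can keep baseline as a response or covariate, and nothing in 10.8.3 forbids this. Model terms for secondary analyses are commonly left to the SAP, which is not at hand. The endpoint could also mean Visit 8 or the whole of follow-up. This largely stands. A reader might infer that the plan ignores the sampling times, or is bound to treat Visit 7 as one time and subtract baseline. The protocol does not say so, and its descriptive tables and PK curves keep the times apart. What remains is that the protocol itself chooses the quantity compared, change to one endpoint, and an SAP that follows it inherits that choice.

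It is also fair that duration will be judged mainly elsewhere: 10.8.2 rests the study objectives on clinical review of summaries and graphs. Those summaries, however, specify no between-arm contrast at 48 or 72 hours.

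The reply is right about size. A reader might take the 5.8-fold fall as evidence of a known loss of precision. It rests on two single-dose lower bounds for concentration, on a log scale although 10.8.4 rules out transformation. The only timed CVF activity result (2.5.3) reports similarly high inhibition at 4 and 24 hours. No decline in activity over 24 to 72 hours is documented.

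The baseline point has almost no force for PK. Plasma and tissue have no pre-dose PK sample, and pre-dose drug in CVF or rectal fluid should be near zero.

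**Conclusion.** The point holds in a limited form, as an improvement to a secondary analysis and not as a demonstrated error.

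- **Baseline, CVF activity.** Comparing changes has 25% to 54% more variance than baseline adjustment at an assumed r of 0.6 to 0.3, with equal variances. The direction does not depend on r, apart from the negligible cost of estimating one slope; the size does.
- **Sampling time.** A contrast pooled over Visit 7 gives no TAF/EVG-v-placebo estimate at 48 or 72 hours, whatever the decay.
- **Standard error.** It is overstated only if activity falls between 24 and 72 hours. The inflation runs from nothing to about 16% in the simulated cases. With balanced groups the pooled average is unbiased and its true precision hardly changes.
- **PK.** Only the sampling-time point applies.

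**What to change.** In section 10.8.3, add a few sentences:

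- **CVF anti-HIV and anti-HSV activity.** Name the baseline visit or visits (Visit 2, Visit 3 or both). Enter Visit 7 as 24, 48 and 72 hours as randomized. Report a TAF/EVG-v-placebo contrast at each time and the average over the three. Constrain the arms to a common baseline mean, or use the pre-dose value as a covariate.
- **PK.** Enter sampling time in the model. No baseline adjustment is needed.
- **Tissue p24 (EVMS only).** Report only the average over the three times.

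This costs some text and a few model terms, with no new samples or visits, and is best settled before unblinding. The downside is that each time-specific contrast has a standard error about √3 = 1.7 times that of the average. These contrasts should be read as estimates with wide intervals, with the average reported beside them.
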